5.1.1.3 Carbidopa capsules

Carbidopa capsules in 12.5 mg, 25 mg and 65 mg strengths will be provided for oral administration. Carbidopa 12.5 mg and 25 mg will be in size 3 hard gelatine white capsules and carbidopa 65 mg will be in size 0 hard gelatine dark green capsules. Carbidopa capsules are manufactured by Orion Corporation, Finland.

The capsules are stored below 30°C.

5.2 Comparator product

5.2.1 Sinemet® 25 mg/100 mg tablet

Sinemet 25 mg/100 mg IR tablets contain 100 mg of levodopa and 25 mg of carbidopa for oral administration. Sinemet 25 mg/100 mg tablets are manufactured by Merck, Sharp & Dohme B.V.

The tablets are stored below 30°C.

5.3 Selection and timing of doses

Overall, MR levodopa strength will be 50, 100 or 150 mg, carbidopa strength will be 12.5, 25 or 65 mg and ODM-104 strength will be 0, 50 mg or 100 mg. Sinemet contains 100 mg of IR levodopa and 25 mg of carbidopa.

The strength of levodopa, carbidopa and ODM-104 will depend on the parallel group (Groups 1-4) the study subject has been assigned to. The doses during the 4 treatment periods are presented in [Table 1](#) in section [3.2](#).

In all parallel groups, depending on the treatment period, carbidopa with or without ODM-104 will be taken 4 times a day during the days 1-6. On day 7 (PK sampling day), carbidopa with or without ODM-104 will be taken at the same time with levodopa 4 times a day. The duration of treatment will be 7 days for carbidopa and ODM-104 and 1 day for levodopa. In one of the periods in Group 4, Sinemet will be taken on day 7 without ODM-104 and on days 1-6, only carbidopa 25 mg will be administered.

The selected strengths and dosing regimens are based on previous PK studies in healthy subjects conducted during ODM-104 development program and other levodopa programs.

Carbidopa and ODM-104 (in treatment periods including ODM-104) will be taken 4 times a day – first dose, 3.5 h, 7 h and 10.5 h doses, for 6 days. The study treatments should be taken

at the same time every day to provide even concentrations of the active ingredients. The recommended study treatment intake times on days 1-6 are 8:00, 11:30, 15:00 and 18:30 h.

Subjects will arrive at the study centre in the evening before day 1 (day -1) and stay at the study centre until the 24 h PK blood sample has been drawn in the morning of day 8. Subjects will take all study treatments at the study centre.

In the evening of day 6, subjects will start fasting for at least 10 h (from around 22:00 h on day 6) before the first morning dose (0 h) at approximately 8:00 h on day 7. Drinking of water is permitted until 1 h before dosing.

The recommended study treatment intake times on day 7 are the same as those on the previous 6 days: 8:00, 11:30, 15:00 and 18:30 h. Study treatments will be ingested with 200 ml of water. Study subjects should maintain an upright position (sitting or standing) for at least 1 h after the study treatment administration and as much as possible during the day until 24:00 h.

On day 7, 150 ml of water will be given 2 h after each dosing. If extra water is needed, the extra amount of consumed water and time of drinking will be recorded on the eCRF. A standard breakfast will be served 1 h, a standard lunch 4.5 h, a standard snack 8 h, a standard dinner 11.5 h and a light night snack 14 h after the first morning dose. If the standard meals are not eaten completely, this will be recorded on the eCRF. Meals should be eaten within 30 min. Meals on days 1-6 will be served at about the same time as on day 7. However, drinking of water is not restricted and there is no 30 min time limit for eating a meal.

Subjects will remain housed in the unit until the morning of day 8, i.e. 24 h after the first dose of levodopa on the previous day.

5.4 Method of assigning study subjects to treatment groups

All subjects screened will be assigned a screening number. To ensure random allocation of the study treatment sequences, all subjects to be randomised into the study will receive the treatment sequence that corresponds to the next consecutive randomisation number in the study. At the study site, subjects will be assigned with next consecutive subject number before first treatment administration. The treatment sequence will be allocated to this subject number when his entry into the first treatment period of the study is confirmed using the dedicated eCRF. The subject is considered randomised at the time when eCRF provides the treatment sequence allocated to the subject.

In case a discontinued subject will be replaced, the replacing subject will receive the same treatment sequence as the subject he is replacing. If replacement subjects will be enrolled, these will be randomised to go through all 4 treatment periods.

In practise, the first subject who made a registration for the study fulfilling all inclusion criteria and none of the exclusion criteria will be dosed first, the next subject will be dosed second and so on. However, precedence will be given to subjects who participate in a study at the site for the first time and for subjects who served as “stand by” during a preceding study. Randomisation will be carried out on the day of the first treatment administration.

The study will be randomised consisting of 4 parallel groups (Groups 1-4). All groups will have a crossover design with 4 treatment periods, each lasting for 8 days.

Randomisation will be performed across all the groups, i.e. the subject entering the study may be randomised to any of the treatment sequences presented in [Table 2](#).

Table 2. Example of the treatment sequences

Group	Sequence	Group	Sequence
1	B1 / C1 / A1 / D1	3	D3 / C3 / B3 / A3
	A1 / B1 / D1 / C1		B3 / D3 / A3 / C3
	D1 / A1 / C1 / B1		A3 / B3 / C3 / D3
	C1 / D1 / B1 / A1		C3 / A3 / D3 / B3
2	C2 / B2 / D2 / A2	4	A4 / D4 / C4 / B4
	D2 / C2 / A2 / B2		C4 / A4 / B4 / D4
	A2 / D2 / B2 / C2		B4 / C4 / D4 / A4
	B2 / A2 / C2 / D2		D4 / B4 / A4 / C4

See [Table 1](#) for definitions of A1-D4

5.5 Blinding

This is an open-label study.

5.6 Emergency procedures

The investigator is responsible for ensuring adequate medical expertise and facilities to handle possible emergency situations during the study. Emergencies will be treated according to the decision of the physician in charge or the investigator when available.

5.7 Prior and concomitant treatments

Concomitant treatments including herbal products, vitamins and dietary supplements are not allowed during the study (within 2 weeks or 5 half-lives of the drug, whichever is longer, before the first study treatment administration until the end-of-study visit). Paracetamol may be taken for the treatment of occasional pain.

In case any concomitant treatment is required during the study, the study subject needs to discontinue the study due to a protocol deviation, if the investigator or sponsor considers that the concomitant treatment could affect the outcome of the study (see section 4.5). The decision will be based on the time the concomitant treatment was taken and the pharmacology and PK of the concomitant treatment.

All concomitant treatments during the study, including the post-treatment period, must be recorded on the eCRF. No other investigational treatment is allowed to be used concomitantly with the study treatment. The study subject must not participate concurrently in any other clinical drug study or have been administered another investigational drug within 60 days before the first study treatment administration.

5.8 Restrictions

Intake of grapefruit, grapefruit juice, bitter orange and bitter orange juice are prohibited during the study (from the screening visit until the end of study visit).

The use of coffee, black and green tea, energy drinks or any other caffeine-containing products is not allowed from 24 h before the first levodopa administration on the PK sampling day (day 7) until the last PK blood sample is taken on the following day. Only moderate consumption of caffeine-containing products is allowed on other study days.

Subjects will be instructed to abstain from consuming alcohol and nicotine-containing products for at least 48 h prior to first dosing in each period and during in-house stay.

If the subject practises intensive physical exercise, it should remain on a stable level during the study. Intensive physical exercise is not allowed from 48 h before first dosing in each period and during in-house stay.

Blood donation and administration of another investigational study treatment are not allowed during the study. Sauna bath is prohibited during in-house stay until 24 h after the last PK blood sample is taken.

See section 6.4.5 for restrictions regarding fasting before safety laboratory tests and section 5.3 regarding fasting and timing of meals related to dosing of study treatments.

See section 5.7 for restrictions regarding concomitant treatments.

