1.3 Benefit-risk assessment

Healthy subjects in this study will not receive any direct health-related benefit from administration of levodopa, carbidopa and ODM-104. However, the study subjects will receive general information on their current health by laboratory tests, electrocardiograms (ECGs), physical examination including blood pressure (BP) and heart rate (HR) measurements.

Levodopa, carbidopa and ODM-104 have been generally well tolerated and safe in previous PK studies (studies 3112001, 3112002 and 3112003) and in an ongoing study (3112004) in patients with PD; however, they are known to cause different symptoms in some subjects. Headache, nausea, nasopharyngitis, flatulence, vomiting, increased blood creatine phosphokinase, constipation and dizziness were reported relatively frequently in previous PK studies with ODM-104. In addition, isolated cases of cardiac conduction abnormalities and mild increases in liver transaminases were reported. No serious adverse events (SAEs) have been reported in previous phase I studies on ODM-104. Based on these findings as well as the nonclinical data on ODM-104, the events of increase in liver tests, cardiac arrhythmias and gastrointestinal irritation are considered as important potential risks for ODM-104. These risks are subject to close monitoring during the clinical program.

Carbidopa single dose used in the test treatments is higher than those in many levodopa treatments on the market with 4 to 1 levodopa to carbidopa ratio. However, the dosing frequency is 4 times a day and the total daily dose of carbidopa will not exceed the daily dose of the approved levodopa products in this study. Higher carbidopa dose has been used in combination with levodopa and ODM-104 in the previous PK studies and in the ongoing study in patients. In the present study subjects remain in the research institute for the whole duration of the dosing period. Samples for laboratory tests and ECG monitoring are applied to exclude subjects with abnormalities from entering the study and after treatment initiation to be discontinued if specified abnormalities emerge. Signs of nausea, gastrointestinal and other symptoms will be followed clinically daily and if intolerable, treatment will be discontinued.

Blood sampling may cause local pain and haematoma as well as fainting in isolated cases. In addition, ECG electrodes attached to the skin may cause irritation.

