6.1.2.2 Days 2-5

The following procedures on days 2-5 will be performed:

- Subjects will take carbidopa and ODM-104 (on study periods including ODM-104) similar to day 1 and as described in section 5.3.
- Meals will be served as described in section 5.3.
- AEs, current medical conditions and concomitant treatments will be recorded.

6.1.2.3 Day 6

The following procedures on day 6 will be performed:

- Subjects will take carbidopa and ODM-104 (on study periods including ODM-104) similar to day 1 and as described in section 5.3.
- HR and BP will be recorded in the supine position after at least 5 min rest 1-2 h after the 7 h dose.
- 12-lead ECG will be recorded in the supine position after at least 5 min rest 1-2 h after the 7 h dose.
- Meals will be served as described in section 5.3.
- Current medical conditions and concomitant treatments will be recorded.
- AEs will be recorded.

6.1.2.4 Day 7

Subjects will fast from 22:00 h (10 h) on day 6 until breakfast on day 7, except that drinking of water is permitted up to 1 h before dose.

- BP and HR will be recorded in the supine position after at least 5 min rest 0-2 h before the first dose and 1-2 h after the 7 h dose.
- 12-lead ECG will be recorded in the supine position after at least 5 min rest 0-2 h before the first dose and 1-2 h after the 7 h dose.
- Blood samples for selected haematology and clinical chemistry tests will be collected before the first dose; see section 6.4.5 for details.
- Urinalysis will be performed.
- C-SSRS will be performed.
- Subjects will take the first dose (levodopa, carbidopa and possible ODM-104) approximately at 8:00 h after the pre-dose PK blood sampling. All study treatments will be taken precisely at the planned time points, including time points coinciding with PK blood sampling; see section 5.3 for details.
- Blood samples for PK assessments will be collected; see section 6.2.1 for details.
- Meals will be served as described in section 5.3.
- AEs, current medical conditions and concomitant treatments will be recorded.

6.1.2.5 Day 8

- Blood sample for 24-h PK assessments will be collected in the morning of day 8; see section 6.2.1 for details.
- Subjects will be instructed to call the study centre when they experience any AE or need to take any concomitant treatment until the end-of-study visit when the subjects are not in-house.
- Subjects can leave the study centre after the 24 h PK blood sample has been collected.

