6.1.3 Procedures during the end-of-study visit

The end-of-study visit will take place 4-21 days after the last study treatment dose. The following procedures will be performed at the end-of-study visit:

- Physical examination will be performed. Weight will be measured and BMI recorded.
- BP and HR will be recorded in the supine position after at least 5 min rest.
- 12-lead ECG will be recorded in the supine position after at least 5 min rest.
- Blood samples for haematology and clinical chemistry tests will be collected. The same haematology and clinical chemistry tests as at the screening visit except thyroid stimulating hormone and albumin will be determined; see section 6.4.5 for details.
- Urinalysis will be performed.
- AEs, current medical conditions and concomitant treatments will be recorded.

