### 7.2.3 Handling of baseline values

Screening visit will be used as a baseline for all post baseline variables. If multiple values of a variable are recorded at screening:

- For safety laboratory measurements the last of these values will be used as baseline.
- For ECG the average of these values will be calculated and used as baseline.

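### The 48 h exercise and alcohol bans cover every in-period chemistry draw but neither the screening baseline nor the end-of-study sample (minor)

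*Protocol*

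**What the plan says.** Protocol 5.8 sets both bans. On exercise: "Intensive physical exercise is not allowed from 48 h before first dosing in each period and during in-house stay". On alcohol, subjects are to "abstain from consuming alcohol and nicotine-containing products for at least 48 h prior to first dosing in each period and during in-house stay". Outside those windows the only exercise rule is: "If the subject practises intensive physical exercise, it should remain on a stable level during the study".

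The in-house stay ends on the morning of Day 8 (protocol 6.1.2.5): "Subjects can leave the study centre after the 24 h PK blood sample has been collected".

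Protocol 6.4.5 puts CK, ALT, AST, ALP, gamma-GT and bilirubin in the screening panel, the Day 1 and Day 7 pre-dose panels of each period, and the end-of-study panel. At the end-of-study visit (6.1.3), "Blood samples for haematology and clinical chemistry tests will be collected". The only condition stated before the screening draw is a 10 h fast (6.1.1, 6.4.5).

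The laboratory baseline is the screening value. SAP 7.2.3: "Screening visit will be used as a baseline for all post baseline variables". SAP 8.5.2 and protocol 8.4.5.3 say the same for laboratory changes.

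The affected tests are ones the protocol singles out. Section 1.3 lists, among other findings, "increased blood creatine phosphokinase, constipation and dizziness were reported relatively frequently in previous PK studies with ODM-104", and names rises in liver tests as an important potential risk under close monitoring.

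**The concern.** A man who trains regularly may keep training up to the screening draw and again before the end-of-study draw, but must stop whenever he is on treatment. Regular drinking within the 21-unit weekly limit of exclusion criterion 12 is in the same position. If exercise or alcohol moves CK or liver tests, enforced rest coincides with treatment, and the screening value is not taken under the conditions of the values compared with it.

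Two readings are exposed. Change from screening to an in-period value mixes any drug effect with the effect of stopping exercise and alcohol. An isolated rise at end of study may have an ordinary cause that the plan does nothing to limit. That second draw has some weight: Day 7 chemistry is taken before the day's first dose, hence before any levodopa in that period, and no chemistry is scheduled on Day 8. After periods 1 to 3, the next period's Day 1 sample follows, under the bans. After period 4 only the end-of-study sample follows, without them.

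**Working it through.** The plan states no figure on this point, so the check sets the ban windows against the draw times.

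Inputs: first dose at about 8:00 and last daily dose at about 18:30 (protocol 5.3); bans from 48 h before first dosing until discharge on Day 8 (5.8, 6.1.2.5); screening up to 21 days before first dose (6.1.1); end of study 4 to 21 days after last dose (6.1.3).

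| Draw | Minimum abstention required | Other stated condition |
|---|---|---|
| Screening (baseline) | 0 h | 10 h fast, breath test |
| Day 1 pre-dose | about 48 h | breath test on admission |
| Day 7 pre-dose | 48 + 6 × 24 = about 192 h | in-house |
| End of study | 0 h | no breath test |

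Unrestricted time before end of study: the bans lapse at about 8:00 on Day 8, which is 13.5 h after the 18:30 dose. The visit falls 96 to 504 h after that dose, leaving 96 − 13.5 = 82.5 h to 504 − 13.5 = 490.5 h. Counted by calendar day the minimum is about 72 h (8:00 on Day 8 to 8:00 on Day 11). A 48 h restriction fits inside either.

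What this does to the comparisons, for one subject and one analyte: let *a* and *b* be the excess from exercise or alcohol at screening and end of study, *r1* and *r7* what remains of it on Day 1 and Day 7, *d* the Day 7 effect of the treatment, and *e* any drug effect left at end of study.

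- Day 7 minus screening = *d* + *r7* − *a*. The excess at screening is subtracted from the drug effect.
- The difference between two treatments in that change = *d*(C) − *d*(A), plus the difference in *r7*, which should average near zero because the in-house rest is the same. The shared *a* cancels within a subject who has both periods.
- Day 7 minus the same period's Day 1 = *d* + *r7* − *r1*. No screening value enters.
- End of study minus screening = *e* + *b* − *a*. With stable habits *b* and *a* are alike on average, but *b* − *a* still varies from man to man.

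None of *a*, *b*, *r1* or *r7* can be obtained from the documents.

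**The case against.** The strongest reply is that the trial already collects what is needed. Day 1 and Day 7 chemistry is drawn under the bans in all four periods, actual values and out-of-range counts by visit are summarised as well as changes, and every group has two treatments without ODM-104 under the same in-house rest. End of study against screening is roughly like for like, since both fall under habitual activity that section 5.8 asks to keep stable. Clinically relevant findings may be rechecked (6.4.5), and causality assessment weighs other explanations (6.4.1.2). The liver-test discontinuation limit in section 4.5 is set against the upper limit of normal, not against baseline. Most of this stands, and it keeps the point minor.

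It does not remove the point. The SAP plans no change from Day 1; its change and shift tables run from screening. Screening values also feed exclusion criteria 3 and 8, which a Day 1 baseline would not help. The stable-level sentence permits training before the two unrestricted draws while the next sentence stops it in-house. A breath test detects only current alcohol, and end of study has none.

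A reader might infer that a true CK rise on treatment would appear as no change. That could be so only for mean change from screening read alone. One could also attach a size: if 3 to 5 of 14 men trained and their CK were multiplied by 1.5 to 3, the arithmetic mean at screening would be inflated by 3/14 × 0.5 = 11% to 5/14 × 2 = 71%. Neither input is in the documents, the upper figure combines both extremes, and the median, which SAP 7.2.12 also reports, would move much less. The range should not be quoted as an estimate.

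Consent must precede screening activities, so a restriction before that draw may seem awkward. The 10 h fast already needs the same advance notice, and section 6.1.1 allows screening on two occasions.

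**Conclusion.** The gap is real and minor. The laboratory baseline and the last scheduled chemistry fall outside bans that cover every scheduled in-period draw, for tests the protocol says it must watch. Changes from screening, and single end-of-study rises, can partly reflect exercise or alcohol. The size cannot be computed from the documents.

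This rests on two assumptions that the documents do not state: that intensive exercise can raise CK and AST and alcohol can raise liver enzymes, and that some subjects train or drink in the days before those two visits. A screening visit that happened to fall within 48 h of first dosing would be covered, but the plan does not require that.

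The documents do not support a claim that an ODM-104 signal would be lost, that treatment comparisons of laboratory values are materially biased, or that the discontinuation limits are distorted. The primary PK analysis is untouched.

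**What to change.** 1. In protocol 5.8, extend the existing 48 h exercise and alcohol restriction to the screening and end-of-study blood draws. Section 5.8 already runs its grapefruit rule from screening to end of study, so the wider span has a precedent. Give the screening instruction with the fasting instruction, or after consent using the two-occasion option in 6.1.1. Give the end-of-study instruction at Day 8 discharge (6.1.2.5) and repeat it in 6.1.3.
2. In SAP 7.2.3 and 8.5.2, add change from the same period's Day 1 pre-dose value for CK and liver tests. The data are already collected under the bans.

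Cost: a few sentences in the protocol and subject information, two further 48 h restrictions per subject, and a few extra tables. No additional samples are needed; splitting screening over two occasions may mean a second attendance for some. A 48 h rule aligns screening and end of study with Day 1, not fully with Day 7, which follows about 192 h of abstention. The added Day 1 comparison has the same 48 h against 192 h difference.

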5.9 Treatment compliance and exposure

All study treatment intakes will be performed in accordance with the specifications of the investigator and under the supervision of study centre personnel. This includes checking the oral and buccal cavity.

Levodopa, carbidopa and ODM-104 concentrations in plasma will indicate that each subject has ingested the study treatments. Any deviation from the treatment regimen must be documented on the eCRF.

The investigator or other study centre personnel is responsible for study drug accountability during the study. The investigator must maintain accurate records demonstrating the date and amount of drug received, to whom and by whom dispensed (drug dispensing list) and accounts of drugs accidentally or deliberately destroyed. At the end of the study, all original containers, whether empty or containing unused products, will be returned to the sponsor for disposal.

